### 11.3 Clinical Laboratory Evaluations

The following hematology and serum biochemistry laboratory tests will be summarized by visit and by the three randomized treatment groups, including a combined column for the two CSL346 groups. The summaries will be provided for the analysis population as described in [Section 11](#). Data for urinalysis will only be listed.

**Hematology:** Hemoglobin, hematocrit, erythrocytes (RBC) count (RBC indices of MCV; MCH; MCHC; RDW, if available), total and differential leukocyte (WBC) counts (neutrophils; neutrophil band forms, lymphocytes; monocytes; eosinophils; basophils), reticulocytes, and platelet count.

**Serum Biochemistry:** Albumin, alkaline phosphatase, alanine aminotransferase (ALT), aspartate aminotransferase (AST), bilirubin (total), bilirubin (direct), blood urea nitrogen (BUN), calcium, carbon dioxide, chloride, creatinine, creatinine kinase, C reactive protein (CRP), glucose, potassium, sodium, protein (total), cholesterol (total), HDL cholesterol, LDL

cholesterol, bicarbonate, Lactate dehydrogenase (LDH), gamma-glutamyl-transferase (GGT), triglycerides, urate (uric acid), international normalized ratio (INR), prothrombin time, and activated partial thromboplastin time (aPTT).

**Urinalysis:** Bilirubin, glucose, nitrites, pH, leukocyte esterase, blood, ketones, urobilinogen, protein, and specific gravity.

Standard safety laboratory data from the central lab will be presented in SI units (except as presented in [Appendix 16.10](#) and in the order presented as given above. Measured laboratory values will be summarized descriptively by scheduled visit. Changes from baseline for laboratory parameter will be derived and presented in the same way as measured laboratory values.

Samples for standard urinalysis will be taken at screening and Day 1.

A laboratory value that is outside the reference range is either high abnormal (value above the upper limit of the normal [ULN] reference range) or low abnormal (value below the lower limit of the normal [LLN] reference range). An abnormal laboratory value is not necessarily of potential clinical interest. For each of the hematology and chemistry lab tests, shift tables will be constructed to compare the individual subject baseline value with respect to the normal range to their Week 24 (or last observed value for dropouts before Week 24) value with respect to the normal range.

The incidence of potentially clinically significant abnormal values for selected laboratory measurements will be summarized by visit during the Treatment Period and Follow-up Period. [Table 3](#) gives the ranges of potential clinical concern for selected laboratory measurements.

The denominator in percentage calculation at a scheduled visit will be based on the number of subjects with a non-missing value at that particular visit.

Mean plots +/- SD over time will be provided for lab parameter of hematology and serum biochemistry. Hy's law plots for AST versus bilirubin (total) and ALT versus bilirubin (total) will be provided.

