Exclusion

Subjects must not have a current diagnosis of type 1 diabetes mellitus, history of acute kidney injury or chronic dialysis/renal transplant, anticipated renal transplant, uncontrolled hypertension or Class III / IV heart failure, left ventricular ejection fraction $< 50\%$ by echocardiogram, troponin-I $>$ the upper reference limit, b-type natriuretic peptide (BNP) $> 200 \text{ pg/mL}$, or alanine transaminase $> 2x$ the upper limit of normal.

Study Product Dose, Dosing Regimen, and Administration

CSL346 is supplied as a sterile solution for IV and SC infusion at a concentration of 100 mg/mL .

All CSL346 doses will be calculated based on weight and normalized to a standard volume with sterile normal saline. CSL346 will be administered at an initial loading dose of 3 mg/kg or 6 mg/kg IV in the arm, followed by 8 mg/kg or 16 mg/kg SC, respectively, in the abdomen at least 2 hours but no more than 6 hours later. Subsequent SC infusions (8 mg/kg or 16 mg/kg per dose) will be administered every 4 weeks for 12 weeks.

Comparator Product, Dose, Dosing Regimen, and Administration	Placebo consists of normal saline for IV and SC infusion. Dosing administration, regimen, and volume will be matched to CSL346.
Efficacy Assessments	The efficacy of CSL346 will be assessed based on changes in ACR associated with CSL346 treatment. To minimize intrasubject variability, baseline values for these parameters will be based on the geometric mean values from 3 first morning void (FMV) urine collections on 2 separate occasions (ie, 6 total FMV samples) before the first dose of IP. On-treatment assessments of ACR will be the geometric mean values from multiple FMV collections at each time point. Only 2 FMV samples will be collected at Visit 9 because a timed 24-hour sample will also be collected at this Visit. The Follow-up assessment of ACR performed for the primary analysis 4 weeks after the last dose of IP (Visit 10) will be based on the geometric mean of 3 FMV samples. For the EOS Visit, the assessment of ACR will also be based on the geometric mean of 3 FMV samples.
Safety Assessments	The safety and tolerability of CSL346 will be based on the following: 
 • AEs (including AESIs) • Vital signs • Physical examinations • 12-lead electrocardiograms • Clinical laboratory assessments (urinalysis, hematology, biochemistry, troponin-I, BNP, SCr, and eGFR)

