12-lead electrocardiogram ^G	X		X	X	X	X	X	X	X	X	X
Echocardiogram ^H	X										
Troponin-I and BNP	X		X	X	X	X	X	X	X	X	X
Coagulation (PT / INR and aPTT)	X										
HbA1c	X			X						X	X
Hematology and biochemistry	X	X ^I	X	X	X	X	X	X	X	X	X
Urinalysis	X			X							
Timed 24-hour urine ^J	X				X				X		
First morning void urine ^K			x3	x3		x3	x3	x3	x2	x3	x3
Morning midstream urine ^L			X	X			X	X		X	
SC normal saline test infusion		X									

Study Period	Screening		Lead-in	Treatment						Follow-up	
	1	2		3	4	5	6	7	8	9	10
Week	Up to –6 weeks		–1	NA	1	2	4	8	12	16	24
Study Day	≤ 63 days ^A before Day 1	–21	–7	1	8	15	29	57	85	113	169
Visit Window (Days)	NA	± 7	± 4	NA	± 3	± 3	± 3	± 5	± 5	± 7	± 7
Randomization				X							
IRT IP assignment				X			X	X	X		
IP administration ^M				IV and SC			SC	SC	SC		
Serum PK sampling ^N				X	X	X	X	X	X	X	X
Local tolerability assessment				X	X	X	X	X	X	X	
Adverse events	From ICF Signature through Last Visit										
Concomitant medications	From ICF Signature through Last Visit										
Immunogenicity				X			X	X		X	
Biomarker sample (blood) ^O			X	X			X	X		X	

ACR = albumin-to-creatinine ratio; aPTT = activated partial thromboplastin time; BNP = b-type natriuretic peptide; BP = blood pressure; EOS = End of Study; FCBP = female subjects of childbearing potential; HbA1c = hemoglobin A1c; ICF = informed consent form; IMP = investigational medicinal product; INR = international normalized ratio; IP = investigational product; IRT = interactive response technology; IV = intravenous; NA = not applicable; PK = pharmacokinetic; SC = subcutaneous; PT = prothrombin time.

Notes to the Schedule of Assessments:

- A:** Screening Visit 1 should be performed within 6 weeks before Screening Visit 2.
- B:** Randomization criteria will include evaluations of BP, serum creatinine, and troponin (see [Section 4.1.3](#) for detailed guidance).
- C:** A serum pregnancy test will be performed at Screening for FCBP; serum or urine pregnancy tests will be performed at all other indicated visits.
- D:** A comprehensive physical examination will be performed at Visit 2 (Day –21) and at EOS. An abbreviated physical examination will be performed for all other indicated visits.

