- E:** Vital signs include BP (systolic and diastolic), body temperature, and pulse rate. Blood pressure measurements should be taken in triplicate before all other assessments. Vital signs in general will be collected before any blood samples that are collected at the same time point. At Visit 2 (Day –21), BP will be the only vital sign collected. Instructions for measuring BP will be provided in the Manual of Operations. At Visit 4 (Day 1), vital sign measurements will be taken predose, at 30, 60, and 120 minutes (± 15 minutes) after the first IV dose of IP (before the first SC dose of IP) is administered, then at 30 and 60 minutes (± 15 minutes) after SC dosing.
- F:** Height will be measured at Screening only.

- G:** Electrocardiograms must be performed in triplicate before any blood samples that are collected at the same time point.
- H:** A local assessment of echocardiogram will be performed during Screening unless an echocardiogram was performed for non-study-related reasons within 3 months before Screening.
- I:** At Visit 2 (Day -21), a blood sample will be collected for determination of serum creatinine only.
- J:** A timed 24-hour urine sample will be collected to assess eligibility (ACR) at Screening (Baseline), and to measure CSL346 levels in urine at subsequent indicated visits.
- K:** Subjects will collect urine from their first morning void on 3 consecutive days (2 consecutive days for Visit 9) leading up to and including the morning of each indicated visit.
- L:** Morning midstream urine samples will be collected to evaluate exploratory biomarkers and will also be stored for future research analyses.
- M:** Specific instructions for administration of IP are provided in the IMP Handling Manual. At Visit 4 (Day 1), an initial loading dose of IP will be administered by IV, followed at least 2 hours (but no more than 6 hours) later by the subject's normal prescribed dose by SC infusion. Subsequent doses of IP will be administered by SC infusion.
- N:** Serial blood samples for PK will be collected at Visit 4 (Day 1) predose, at 30 (\pm 5 minutes), 60 (\pm 10 minutes), and 120 (\pm 10 minutes) minutes after the first IV dose of IP (before the first SC dose of IP) is administered, then after the final vital signs measurement. Single PK samples will also be collected at all subsequent visits (before treatment on SC dosing days).

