An overview of identified and potential risks and planned risk mitigation in this phase 2a study is provided in Table 1.

Table 1 Risks and Risk Mitigation

Risk	Potential/ Identified	Source	Risk Mitigation
Injection site reactions	Identified	CSL346_1001 data on file	
 Assessment at study visits Guidance for managing local intolerance
Hypersensitivity / anaphylaxis and infusion reactions; antibody formation	Potential	Class effect of humanized proteins	
 Standard measures Measurement of baseline, mid-, and end of study anti-CSL346 antibody
Weight gain	Potential	Knock-out mouse model [Hagberg et al, 2010]	
 Monitor at study visits
Congenital disorders	Potential	Knock-out mouse model [Bellomo et al, 2000] Preclinical study in quails [Tomanek et al, 2006]	
 Inclusion / exclusion criteria Contraception requirements Pregnancy testing Nonclinical studies in later phases
Renal: acute reversible effect on GFR and / or chronic kidney injury	Potential	Theoretical risk due to VEGF-A modulation [Kamarzarian et al, 2018; Izzedine et al, 2010]	
 Inclusion / exclusion criteria Staged approach for enrollment of subjects with moderate renal impairment Frequent monitoring in first 4 weeks of treatment Measure SCr and evaluate albuminuria at each visit Guidance for managing increases in SCr and albuminuria

Risk	Potential/Identified	Source	Risk Mitigation
Cardiac: myocardial dysfunction with chronic dosing	Potential	Knock-out mouse model [Bellomo et al, 2000] Streptozotocin model [Lal et al, 2017] Theoretical risk due to VEGF-A modulation [Touyz et al, 2018]	
 Exclusion criteria, including baseline assessment of LVEF by ECHO Treatment with SOC Baseline and periodic ECG, BNP, and troponin levels Guidance for managing increases in troponin levels
Increased BP	Potential	Theoretical risk due to VEGF-A modulation [Touyz et al, 2018]	
 Exclusion criteria BP measurement Guidance for managing increases in BP

BP = blood pressure; BNP = b-type natriuretic peptide; ECG = electrocardiogram; ECHO = echocardiogram; GFR = glomerular filtration rate; LVEF = left ventricular ejection fraction; SCr = serum creatinine; SOC = standard of care; VEGF = vascular endothelial growth factor.

2 Study Objectives and Endpoints

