4.1.2 Exclusion Criteria

Subjects must not be enrolled into the study if they meet any of the following exclusion criteria:

1. Current diagnosis of type 1 diabetes mellitus.
2. Known medical history or clinical evidence suggesting non-diabetic renal disease, except for concomitant hypertensive nephrosclerosis or a single kidney.
3. History of acute kidney injury (AKI) within 1 year before Screening and change in SCr from Visit 1 to Visit 2 (Day -21) > 0.3 mg/dL (26.5 µmol/L) by central laboratory assessment.
4. History of chronic dialysis or renal transplant; active on a kidney transplant waiting list (awaiting transplant) with a living donor identified, or anticipated transplant within 6 months following randomization in the study.

5. Requirement for concomitant treatment with any prohibited concomitant medication, as indicated in [Section 7.3](#).
6. Uncontrolled hypertension defined as: SBP > 160 mmHg or DBP > 100 mmHg. See also Randomization Criteria ([Section 4.1.3](#)).
7. New York Heart Association heart failure Class III or IV within 1 year before Screening.
8. Myocardial infarction, unstable angina, revascularization procedure (eg, stent or bypass graft surgery), cerebrovascular accident, transient ischemic attack, or new clinically important electrocardiogram (ECG) findings within 6 months before Screening, or a revascularization procedure is planned during the study.
9. Left ventricular ejection fraction (LVEF) < 50% by echocardiogram (ECHO).
An ECHO performed for non-study-related reasons within 3 months before Screening can be used to satisfy this criterion.
10. Troponin-I levels > upper reference limit (URL). See also Randomization Criteria ([Section 4.1.3](#)).
11. B-type natriuretic peptide (BNP) > 200 pg/mL.
12. Alanine transaminase > 2x the ULN.
13. Subject is unable to tolerate SC test infusion.
14. Pregnant, breastfeeding, or not willing to cease breastfeeding.
15. History of cancer within 5 years before Screening, with the following exceptions:
 - Basal cell carcinoma of the skin
 - Squamous cell carcinoma of the skin
 - Carcinoma in-situ of the cervix
 - Carcinoma in-situ of the breast
 - Incidental histologic finding of prostate cancer (Stage T1a or T1b using TNM clinical staging)
16. Positive viral test result for hepatitis B virus (HBV) ([Appendix 2](#)), hepatitis C virus, or human immunodeficiency virus -1 / -2 at Screening.

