8.1.1 Demographics and Safety Assessments

Subject demographics and safety assessments to be conducted during this study are provided in Table 6. Clinical laboratory assessments are to be performed at time points as detailed in the [Schedule of Assessments](#). The time windows for each type of assessment are detailed in [Section 8.6.1](#).

Table 6 Study Procedures: Demographics and Safety Assessments

Assessment	Description
Demographics	
 Year of birth / age Sex Race Ethnicity (where permitted)
Medical History	
 Relevant medical history within 12 months before Screening Diagnosis and disease status Concomitant and prior medications Contraception method (if relevant)
Pregnancy Test	
 Serum and / or urine tests for beta-hCG
Virology	
 HIV HBV HCV 
(Appendix 2)

Physical Examination (full or abbreviated)	
 As per the site's standard procedure
12-lead ECG (triplicate)	
 Heart Rate PR Interval QRS Duration QT Interval QTcB Interval QTcF Interval Investigator's overall interpretation
Echocardiogram	
 To assess LVEF; Assessed locally as part of subject's eligibility evaluation during Screening. An ECHO performed for non-study-related reasons within 3 months before Screening can be used.
Troponin-I ^a	
 For evaluation of potential cardiac toxicity
BNP	
 To assess signals of potential cardiac toxicity
Adverse Events	
 Evaluation of all adverse events (eg, causality / relatedness, severity, seriousness) Adverse events of special interest (Section 9.1.3)
Vital Signs	
 Blood pressure (systolic and diastolic) Body temperature Pulse rate
Height and Weight	
 Height at Screening only
Urinalysis (Screening and Visit 4 / Day 1 only)	
 Bilirubin Specific gravity Glucose Blood Nitrites Ketones pH Urobilinogen Leukocyte esterase Protein
Hematology	
 Leukocytes (WBC count)

Assessment	Description

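### The SAP specifies no group-level summary of BNP, one of three cardiac safety markers named in the protocol and drawn at all seven post-dose visits

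*SAP*

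**What the plan says.** Protocol Table 1 (Section 1.4) lists myocardial dysfunction with chronic dosing as a potential risk. Its mitigations include "Baseline and periodic ECG, BNP, and troponin levels". The synopsis names BNP as a safety laboratory measure in its own right, apart from hematology and biochemistry: "Clinical laboratory assessments (urinalysis, hematology, biochemistry, troponin-I, BNP, SCr, and eGFR". Protocol Table 6 (Section 8.1.1) gives the purpose of BNP as "To assess signals of potential cardiac toxicity" and that of troponin-I as "For evaluation of potential cardiac toxicity". The Schedule of Assessments gives the pair one row, "Troponin-I and BNP", marked at every visit except Visit 2, where "a blood sample will be collected for determination of serum creatinine only".

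SAP 11.3 opens its summaries with "The following hematology and serum biochemistry laboratory tests will be summarized by visit and by the three randomized treatment groups" and then names the tests. Neither BNP nor troponin-I is named. Shift tables are promised for the hematology and chemistry tests, and mean plots for hematology and serum biochemistry. SAP Table 3 counts troponin-I above the upper limit of normal and has no BNP row. The section ends by promising a by-subject listing of all laboratory values, with flags for values out of range.

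**The concern.** BNP is collected repeatedly to look for a cardiac signal, and the SAP specifies no output in which the arms could be compared on it. A modest rise across an arm, with each subject's value unremarkable alone, is the pattern that listings and investigator judgement are least likely to reveal and that a by-visit table would show.

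The other cardiac outputs do not fill this gap. ECG is summarised fully but measures something different. Troponin-I uses a conventional rather than a high-sensitivity assay (Protocol Table 6, footnote a) and is tabulated only as above or not above a limit. Echocardiography is scheduled only at Screening. What is at stake is the completeness of the cardiac safety read-out in what the SAP calls the first study in subjects with type 2 diabetes. The primary efficacy result is not affected.

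**Working it through.** The plan gives no figure to reproduce. The check is a count of scheduled draws and a search of the SAP for any output that covers them.

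**Draws.** In the Schedule of Assessments the BNP row is marked at Visits 1, 3, 4, 5, 6, 7, 8, 9, 10 and End of Study: 10 of 11 visits. Visit 4 is drawn before dosing. The post-dose draws are therefore Visits 5 to 10 and End of Study (Weeks 1, 2, 4, 8, 12, 16 and 24), which makes 7.

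**Volume.** 100 subjects × 7 = 700 post-dose values at most, at the planned sample size. If the assumed 6% drop-outs gave none and the rest missed no draw, 94 × 7 = 658.

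**Specified outputs for the three markers in Protocol Table 1:**

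| SAP output | ECG | Troponin-I | BNP |
|---|---|---|---|
| Values and changes by visit and arm | Yes (11.4.3) | Not named | Not named |
| Threshold count by arm | Yes (Table 5) | Yes, > ULN only (Table 3) | None |
| Shift table or mean plot (11.3) | Not named | Not named | Not named |
| Model, PK/PD plot or test direction (10, 14, 16.9) | Not named | Not named | Not named |
| By-subject listing | Yes (11.4.3) | Yes (11.3) | Yes (11.3) |

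BNP occurs in the SAP only in the schedule copied into Appendix 16.8 and its abbreviation key. SAP Section 5, which records changes from the protocol, says nothing about it. The exploratory biomarker lists in SAP 4.1.4 are open-ended, but they do not name BNP, and BNP has its own schedule row separate from the biomarker samples.

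**Is the omission deliberate?** SAP 11.3 names INR, prothrombin time and aPTT for by-visit summary, although coagulation is scheduled only at Screening. A group of tests with no scheduled post-dose value is on the list, while a test with seven post-dose draws is not. That looks more like an oversight than a decision.

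**The case against.** The strongest reply is that SAP 11.3 also contains a general sentence promising descriptive summaries of measured laboratory values by scheduled visit, followed by changes from baseline. Table 3 includes ACR and troponin-I, neither of which is on the named list, so the section does reach beyond that list. This has some force. But the general sentence directly follows one that ties the presentation to the order of the tests already listed, and that list has no BNP. The wording is at best ambiguous, and the narrow reading is the more natural one.

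Second, the table shells and the SAP for the data monitoring committee are separate documents that were not available here, and either may contain BNP output. That stands as a limit on this check. Even so, SAP Section 3 presents itself as the complete description of the final analysis, so the specification belongs there.

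Third, BNP is not an endpoint, and Protocol 10.3.3 plans no BNP analysis. A reader might infer that the SAP dropped a promised analysis. It did not: the mismatch is with the stated purpose of collecting BNP.

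Fourth, a reader might infer that a BNP signal could reach no table at all. That goes too far. Protocol 9.1.1 requires laboratory changes judged clinically significant to be recorded as adverse events. The cardiac event of special interest is defined openly enough to include BNP (SAP 11.2). Both feed the adverse event tables. What those routes cannot show is a shift between arms made up of individually unremarkable values.

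**Conclusion.** The point holds in this form: the SAP as written specifies no by-visit summary, shift table, plot or threshold count for BNP, and only a threshold count for troponin-I. A group-level BNP shift would appear in no specified summary table. This rests on the narrow reading of SAP 11.3 and on the SAP alone.

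Two stronger readings should be resisted. BNP is not the protocol's sole cardiac marker: ECG and troponin-I stand beside it, and troponin-I is the one with stopping criteria (Protocol Table 13).

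Nor do the documents support a claim about how small a BNP rise the trial would detect, because they give no SD for change in log BNP. As an assumed range, take SD 0.4 to 0.7 with 47 subjects per group and a two-sided 5% test. The standard error is SD × √(2/47), and power is approximately Φ(ln(ratio)/SE − 1.96):

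- SD 0.4: SE = 0.083. For a 30% rise, 0.262/0.083 ≈ 3.2, so power is about 89%.
- SD 0.7: SE = 0.144. For a 30% rise, 0.262/0.144 = 1.82, so power is about 44%. For a 35% rise, 0.300/0.144 = 2.08, so power is about 55%.

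Across that range the answer runs from good power to a coin toss. The case for the tables rests on completeness of safety reporting and does not need a power claim. It is worth correcting because the data are already being collected and the change costs almost nothing.

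**What to change.** In SAP 11.3:

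- Add BNP and troponin-I to the tests summarised by visit, as values and change from baseline, for 8 mg/kg, 16 mg/kg, combined CSL346 and placebo. The default baseline rule in SAP 8.2.3 already covers both.
- If BNP is skewed, summarise it on the log scale as the geometric mean ratio to baseline.
- Add BNP to the shift tables against its reference range. Those tables compare baseline with Week 24, twelve weeks after the last scheduled dose, so the by-visit summary is the more informative addition.
- If a BNP row is added to Table 3, the sponsor should state and justify the reporting cut-off. The protocol's only BNP figure, "B-type natriuretic peptide (BNP) > 200 pg/mL", is an entry exclusion, and nothing in the documents supports carrying it over to on-treatment values.

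A repeated-measures model for BNP is optional; descriptive tables would close the gap. If BNP is already in the table shells, a sentence in 11.3 saying so is enough.

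The cost is SAP wording and a few tables. There are no new samples, visits or staff, and no dosing, stopping or management rule changes.

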9.1.3.2 Serum Creatinine

The criteria for increases in SCr due to AKI are based on a definition of AKI that incorporates absolute changes in SCr over a 24- to 48-hour period (Waikar and Bonventre, 2009). The percent changes in SCr after severe AKI are highly dependent on baseline kidney function. In contrast, the absolute increases in SCr are nearly identical across the spectrum of baseline kidney function. Conservative criteria were identified to trigger a comprehensive evaluation that balances the safety of subjects enrolled in the study with small changes in SCr expected due to intrasubject variability.

An SCr AESI is defined as a confirmed increase from Baseline of at least 0.3 mg/dL. All cases meeting the criteria shown in Table 12 will be specifically reviewed with the IDMC during regularly scheduled safety review meetings.

Table 12 **Increases in Serum Creatinine**

Serum Creatinine – Increase from Baseline (Confirmed)	Investigator Assessment	Action
≥ 0.3 to < 0.7 mg/dL (≥ 26.5 to < 61.9 μmol/L)	Expected changes due to IP-related activity	Continue IP with increased monitoring
≥ 0.7 mg/dL (≥ 61.9 μmol/L)	Reversible episode of AKI unrelated to IP	Withhold IP until serum creatinine returns to baseline
	IP related	Permanently discontinue IP

AKI = acute kidney injury; IP = investigational product.

If a subject has an increase in SCr that meets criteria outlined in Table 12 at any visit while receiving IP, the Investigator will complete an eCRF reviewing possible causes of AKI not related to IP such as volume depletion, urinary tract infection, and exposure to a nephrotoxic agent. Any identified possible reversible causes of AKI not related to IP will be addressed promptly according to local standards of care. A second measurement will be obtained as soon as possible within a maximum of 1 week. If the specified increase is confirmed, the Investigator will obtain a third SCr value within 1 week and update the eCRF.

The Investigator will contact the Medical Monitor who will assist with evaluation and determination of appropriate action to be taken. This consultation will help discern signs of

possible AKI not related to IP from hemodynamically mediated effects on SCr / eGFR potentially associated with IP-related activity, reversible causes of AKI not related to IP or from renal intrinsic injury related to IP.

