### 8.2.5 Multiple Assessments

All data will be reported according to the nominal visit date for which they were reported (that is, no visit windows will be applied during dataset creation and the visit will not be re-allocated if the actual visit date deviates from the planned date according to the visit schedule in the protocol). In the instance of early discontinuation from the study, data collected at discontinuation from study should be slotted to the closest scheduled visit.

Unscheduled data will not be included in by-visit summaries, but will contribute to values of clinical importance and will appear chronologically in listings. Data from all assessments (scheduled and unscheduled), including multiple assessments, will be included in listings.

If multiple assessments on different days are reported for the same scheduled assessment, then the latest assessment for that scheduled assessment will be analyzed unless as specified otherwise below.

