**Table 3 Laboratory Values of Potential Clinical Importance**

Laboratory Parameter	Potential Clinical Importance Range	Unit
ACR (Urine)	Change from baseline $\geq 1.5$	mg/g
Platelet Count	<40 or >999	$10^3$ /UL
Hematocrit	<20 or >60	%
Hemoglobin	<7 or >20	g/dL
White Blood Cell Count (WBC)	<3 or >20	$10^9$ /L
Neutrophil Count	<1.5	$10^9$ /L
Serum Creatinine	Change from baseline (>0.3 and <0.7) OR Change from baseline $\geq 0.7$	mg/dL
Fasting Glucose	<70 or $\geq 250$	mg/dL
Nonfasting Glucose	<40 or >450	mg/dL
Potassium	<3 or $\geq 5.5$	mEq/L
Troponin-I	>ULN	ng/mL
Alkaline phosphatase	>2 x ULN	U/L
Total bilirubin	>2 x ULN	$\mu$ mol/L
ALT/SGPT	>3 x ULN	U/L
AST/SGOT	>3 x ULN	U/L

A by-subject listing of all laboratory values including flag for values out of normal range and clinical importance will be provided. Listings will include in general all visits (scheduled and unscheduled).

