## 11.4.2 Vital Signs

The vital signs will be summarized by visit and by the three randomized treatment groups and a combined CSL346 treatment group. The summaries will be provided for the analysis population as described in [Section 11](#).

The following summaries will be provided for systolic and diastolic blood pressure, heart rate, body temperature and body weight:

- Values of vital signs by scheduled visit,
- Change from baseline by scheduled visit.

Vital signs will be assessed as a triplicate measurement. For purpose of analysis the mean value of such triplicate parameter assessments will be used.

Vital sign values of potential clinical importance will be determined by using the criteria detailed in Table 4. The number and percentage of subjects with vital signs of potential clinical importance will be summarized by visit and at any time for the three randomized treatment groups and a combined CSL346 treatment group.

A by-subject listing of all vital sign data (scheduled and unscheduled visits) will also be presented. The listing will include a flag for values of potential clinical importance.

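### SAP 11.3 gives unscheduled laboratory values no place in the clinical-importance table, although SAP 8.2.5 says they count; the Table 3 creatinine flag also skips a rise of exactly 0.3 mg/dL

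*SAP*

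**What the plan says.** SAP 11.3 sets the layout of the laboratory clinical-importance table: "The incidence of potentially clinically significant abnormal values for selected laboratory measurements will be summarized by visit during the Treatment Period and Follow-up Period". The percentages follow the same layout: "The denominator in percentage calculation at a scheduled visit will be based on the number of subjects with a non-missing value" at that visit. Nothing in 11.3 asks for a count over the whole post-baseline period.

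SAP 8.2.5 governs unscheduled results across all assessments: "Unscheduled data will not be included in by-visit summaries, but will contribute to values of clinical importance and will appear chronologically in listings". It adds a rule for repeats filed under a planned visit: "If multiple assessments on different days are reported for the same scheduled assessment, then the latest assessment for that scheduled assessment will be analyzed", unless specified otherwise.

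For vital signs, SAP 11.4.2 says that subjects with values of potential clinical importance "will be summarized by visit and at any time for the three randomized treatment groups" and for the combined CSL346 group. SAP 11.4.3 uses the same layout for ECG.

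For creatinine, SAP Table 3 has two bands. The lower one is "Change from baseline (>0.3 and <0.7" mg/dL) and the upper one starts at 0.7 mg/dL. Protocol 9.1.3.2 says: "An SCr AESI is defined as a confirmed increase from Baseline of at least 0.3 mg/dL". Protocol Table 12 and the AESI definition in SAP 11.2 also start at 0.3 inclusive.

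**The concern.** Renal, cardiac and hepatic laboratory changes are among the main safety questions of this study, and the protocol generates off-schedule results for them. A flagged creatinine is repeated within a week and, if confirmed, measured a third time (Protocol 9.1.3.2). A raised troponin is repeated within 48 hours (Protocol 9.1.3.5). Other abnormal central-laboratory results judged clinically significant are repeated promptly (Protocol 8.1.1).

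If the only value beyond a Table 3 cut, or the highest one, comes from such a draw, a programmer following 11.3 has no row for it. The table also cannot answer the simplest safety question, which is how many subjects in each arm ever crossed the threshold.

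The creatinine mismatch is separate and smaller. A subject can meet the numerical AESI criterion and fall in neither Table 3 band.

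**Working it through.** No planned figure is at issue, so the check sets the sections side by side and then tests the creatinine bound.

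**1. Where can an unscheduled value be counted?**

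| Data type | Section | By-visit rows | At-any-time row |
|---|---|---|---|
| Vital signs | SAP 11.4.2 | yes | yes |
| ECG | SAP 11.4.3 | yes | yes |
| Laboratory | SAP 11.3 | yes | none specified |

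SAP 8.2.5 bars unscheduled values from the by-visit rows of all three. For vital signs and ECG the second half of its sentence can be met through the at-any-time row. For laboratory data the only place left in 11.3 is the flagged listing.

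**2. Can a per-subject incidence be rebuilt from the by-visit rows?** The schedule has seven post-baseline visits with chemistry (Visits 5 to 10 and EOS). Let the visit rows count c1 to c7 abnormal subjects. The number ever abnormal at a scheduled visit lies between max(c1,…,c7) and c1+…+c7 (capped at the arm size). The rows do not say where. Subjects abnormal only at unscheduled draws come on top of that.

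**3. Do the other outputs fill the gap?**
- *Repeats filed under a planned visit* do enter the visit row, but under 8.2.5 the latest value is used. A lower repeat on another day replaces the value that crossed the cut.
- *AESI tables* (SAP 11.2) are built from what the investigator marks. The creatinine criterion needs confirmation and the cardiac one needs a clinically meaningful change. The Table 3 flags need neither.
- *Liver tests* have no AESI category. Yet Table 3 uses ALT >3 × ULN and total bilirubin >2 × ULN, the same cuts that appear in the Hy's law criterion of Protocol 3.7.1. The Hy's law plots in 11.3 are not counts, and the SAP does not say whether they use unscheduled values.
- *Shift tables* (SAP 11.3) compare baseline with Week 24 for completers, 12 weeks after the last dose, so they do not show an on-treatment peak.

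**4. Size of one uncounted subject.** With 25 planned per active arm, 1/25 = 4 percentage points. With 50 in the combined CSL346 group or placebo, 1/50 = 2 points.

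**5. The creatinine bound.** For a change of exactly 0.3 mg/dL, 0.3 > 0.3 is false and 0.3 ≥ 0.7 is false, so Table 3 does not flag it. 0.3 ≥ 0.3 is true, so the AESI threshold is met if the rise is confirmed.

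Rounding matters as well. SAP 16.10 converts µmol/L to mg/dL by dividing by 88.4.
- 26.5/88.4 = 0.2998 mg/dL. The protocol's own µmol/L equivalent of the lower cut is just below 0.3, and fails both > 0.3 and ≥ 0.3 if compared unrounded.
- 61.9/88.4 = 0.7002 mg/dL, so the upper cut is not affected.
- In ordinary floating-point arithmetic 1.3 − 1.0 evaluates to slightly more than 0.3 and 1.2 − 0.9 to slightly less. Without a rounding step, equal changes can be classed differently.

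**6. How often would a change equal exactly 0.3?** The documents give neither the SD of creatinine change nor the reporting precision. As an assumption only, take changes normal with mean 0 and SD s, recorded in steps of g. The share of rises ≥0.3 that sit exactly on 0.3 is [Φ((0.3+g/2)/s) − Φ((0.3−g/2)/s)] / [1 − Φ((0.3−g/2)/s)]. For s from 0.1 to 0.3 and g from 0.005 to 0.1 mg/dL it runs from about 2.5% (s = 0.3, g = 0.005) to 96% (s = 0.1, g = 0.1). The range is too wide to be a size estimate. It shows only that the answer depends on rounding.

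**The case against.** A reader might infer that confirmatory creatinine, troponin and liver results never reach any table and survive only in a listing. The documents do not support that. Investigator-marked AESIs are tabulated per subject without restriction to scheduled visits (SAP 11.2). Protocol 9.1.1 requires laboratory values judged clinically significant to be recorded as adverse events, so an unscheduled ALT of that kind enters the adverse-event tables. Repeats filed under a planned visit enter that visit's row.

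Confirmatory draws are also a weak example in general. They follow a value that has already crossed the threshold. If that value came from a scheduled visit and remains its record, the subject is already counted. The gap concerns subjects whose only qualifying value, or whose peak, is unscheduled, and those whose first value is replaced by a later one.

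The intent is on the SAP's side as well. Section 8.2.5 says unscheduled values count, and section 3 places table shells in a separate document that is not available here, so an any-time row may already be planned. Oversight does not depend on this table either: the IDMC reviews the creatinine cases meeting Protocol Table 12 and has its own analysis plan. On creatinine, Table 3 drives only a descriptive flag and cannot remove a case from the AESI tables.

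All of this stands, and it limits the point. It does not remove it. Adverse-event and AESI tables rest on investigator judgement and do not give the frequency of crossing a laboratory threshold. Section 11.3 still differs from its two sister sections with no reason given. Liver tests have the weakest alternative route.

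**Conclusion.** The point holds as an internal inconsistency between SAP 8.2.5 and 11.3. Off-schedule laboratory values have no defined place in the clinical-importance table, and 11.3 specifies no per-subject ever-abnormal incidence. It is a descriptive safety-reporting gap that leaves the primary analysis untouched.

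Its size in subjects is unknown, because the documents give no abnormality rates and no frequency of unscheduled draws. A reader might go further and infer that the comparison between arms is distorted by some calculable amount. That is not supported: the rule is the same in every arm, and any percentage would come from an assumed rate. What can be said is that in arms this small a single uncounted subject is visible.

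The creatinine mismatch is real and looks clerical, since Table 3 otherwise follows the two bands of Protocol Table 12. It concerns the reporting flag only; no view is taken here on the protocol's management rules.

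The conclusion assumes that the separate table shells do not already contain an any-time row. If they do, the SAP text needs only to say so.

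**What to change.** In SAP 11.3, add for each Table 3 parameter a row for any time post-baseline, scheduled or unscheduled, shown for each arm and for combined CSL346. The denominator is subjects in the Safety Analysis Set with at least one post-baseline value of that parameter. State that every post-baseline value counts toward this row, including one superseded under the latest-assessment rule in 8.2.5. Say also whether the Hy's law plots use unscheduled values.

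Reconcile the lower creatinine bound in Table 3 with the definition in Protocol 9.1.3.2, Protocol Table 12 and SAP 11.2. State the unit and the number of decimals to which the change is rounded before it is compared with the cut.

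The cost is a few sentences in the SAP, one symbol and one extra row per parameter. No new data are needed, and the layout already exists for vital signs and ECG.
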